#### **11.7.2 Action to Be Taken if Pregnancy Occurs**

The investigator will notify Heat Biologics, or designee, within one week of learning of a patient's pregnancy. The patient will also be followed to determine the outcome of the pregnancy. Information on

the status of the mother and child will be forwarded to Heat Biologics, or designee. Generally, follow-up will be no longer than 6 to 8 weeks following the estimated delivery date. Any premature termination of the pregnancy will be reported.

While pregnancy itself is not considered to be an AE or SAE, any pregnancy complication or elective termination of a pregnancy for medical reasons will be recorded as an AE or SAE (see AE/SAE section of the protocol).

A spontaneous abortion is always considered to be an SAE and will be reported as such. Furthermore, any SAE occurring as a result of a post-study pregnancy and that is considered reasonably related to the investigational product by the investigator will be reported to Heat Biologics. While the investigator is not obligated to actively seek this information in former study participants, he or she may learn of an SAE through spontaneous reporting.

### **11.7.3 Action to be Taken if Pregnancy Occurs in a Female Partner of a Male Study Subject**

The investigator will attempt to collect pregnancy information on any female partner of a male study patient who becomes pregnant while participating in this study. The investigator will record pregnancy information on the appropriate form and submit it to Heat Biologics, or designee, within one week of learning of the partner's pregnancy. The partner will also be followed to determine the outcome of the pregnancy. Information on the status of the mother and child will be forwarded to Heat Biologics, or designee. Generally, follow-up will be no longer than 6 to 8 weeks following the estimated delivery date. Any premature termination of the pregnancy will be reported.

## **11.8 Adverse Events (AE) and Serious Adverse Events (SAE)**

The investigator is responsible for the detection and documentation of events meeting the criteria and definition of an AE or SAE, as provided in this protocol. During the study when there is a safety evaluation, the investigator or site staff will be responsible for detecting, documenting, and reporting AEs and SAEs, as detailed in both this section of the protocol and in the AE/SAE section of the study procedures manual. AEs should only be recorded for up to four weeks following the last dose of study medication, unless the AE is considered related to the study medication, which requires that the AE be reported regardless of the amount of time that has passed since receiving the last dose of study medication.

### **11.8.1 Definition of an AE**

An adverse event is any untoward medical occurrence associated with the use of a medicinal product in humans, whether or not considered related to the medicinal product (21 CFR 312.32 (a)). Note: an AE can therefore be any unfavorable and unintended sign (including an abnormal laboratory finding), symptom, or disease (new or exacerbated) temporally associated with the use of a medicinal product. For marketed medicinal products, this also includes failure to produce expected benefits (i.e., lack of efficacy), abuse, or misuse.

A suspected adverse reaction (SAR) is defined as any AE for which there is reasonable possibility that the drug caused the AE (21 CFR 312.32 (a)).

An AE or SAR is considered unexpected if it is not listed in the Investigator's Brochure or is not listed at the specificity or severity that has been observed or, if an Investigator's Brochure is not required or

available, is not consistent with the risk information described in the general investigational plan or elsewhere in the current application (21 CFR 312.32 (a)).

### 11.8.2 Definition of an SAE

The Code of Federal Regulations (CFR) Title 21 part 312.32 and ICH Guideline for Industry: Clinical Safety Data Management: Definitions and Standards for Expedited Reporting, ICH-E2a March 1995, as implemented by the US FDA, defines a SAE or serious adverse drug experience as any untoward medical occurrence at any dose that:

- Results in death (i.e., the AE actually causes or leads to death)
- Is life-threatening (with regards to determining if an AE is serious, “life-threatening” is defined as an AE for which the patient was at risk of death at the time of the event. It does not refer to an event which hypothetically might have caused death if it were more severe. If either the investigator or the sponsor believes that an AE meets the definition of life-threatening, it will be considered life-threatening)
- Requires inpatient hospitalization or prolongation of existing hospitalization
- Results in persistent or significant incapacity or substantial disruption of the ability to conduct normal life functions
- Results in a congenital anomaly/birth defect
- Results in any “other” important medical event. Medical or scientific judgment should be exercised in deciding whether reporting is appropriate in other situations, such as important medical events that may not be immediately life-threatening or result in death or hospitalization but may jeopardize the subject or may require medical or surgical intervention to prevent one of the other outcomes listed in the above definition. These should also be considered serious. Examples of such events are intensive treatment in an emergency room or at home for allergic bronchospasm, blood dyscrasias, or convulsions that do not result in hospitalization, or development of drug dependency or drug abuse.

### 11.8.3 Disease-Related Events or Outcomes Not Qualifying as SAEs

An event that is part of the natural course of the disease under study (i.e., disease progression) should not be reported as an SAE. Recurrence or progression of the patient’s neoplasia will be recorded in the clinical assessments in the ECRF. Death due to disease progression is to be recorded on the Death ECRF page and not as a SAE. However, if the progression of the underlying disease is greater than what would normally be expected for the patient, or if the investigator considers that there was a causal relationship between treatment with vesigenurtacel-L or protocol design/procedures and the disease progression, then it must be reported as an SAE. Any new primary cancer must be reported as an SAE.

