### **1.3 Description of Investigational Agent Vesigenurtacel-L**

Vesigenurtacel-L is a whole cell vaccine that has been irradiated to render cell replication incompetent while maintaining biological activity, i.e., expression of certain tumor-associated antigens as described above.

Vesigenurtacel-L is derived from a human prostate cancer cell line, PC3. This cell line was evaluated amongst others and was selected based on the overlap of its native antigenic profile with that of tumor

samples from patients with NMIBC. The chosen PC3 tumor cells were modified to express HLA-A1 protein and secrete gp96-Ig fusion protein by stable transfection. Clones with a high level of expression were obtained by G418 (Geneticin) selection and flow cytometry cell sorting.

Preparation of the drug product includes expansion of batches of cells using current good manufacturing practices (cGMP) manufacturing methods. The cells are tested for presence of expression of HLA-A1 by fluorescent-activated cell sorter (FACS) and gp96-Ig expression by enzyme-linked immunosorbent assay (ELISA). Cells are harvested, washed, resuspended in buffered saline, irradiated, washed and vialled. The vialled cells are frozen and then stored at  $\leq -120^{\circ}\text{C}$  in the vapor phase of a liquid nitrogen freezer.

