-  PE at screening and Week 56 (End of Treatment) will have a full examination of body systems and vital signs. Other PE evaluations will be limited to symptoms, weight and vital signs.
-  70mL of heparinized blood, 10mL of non-heparinized blood, and 24mL urine will be collected at the indicated visits.
-  ANA, TSH, ESR, C-reactive protein are required. Other tests (e.g. RF, T3, T4, thyroid antibodies) will be performed only as clinically indicated.
-  All patients will have a cystoscopy/cytology performed at Week 13. If clinically indicated, a repeat biopsy will be performed. Patients with evidence of disease at an assessment may continue on treatment if judged by the investigator to be in the patient's best interest (e.g. would normally receive another course of BCG therapy as SOC). Upon discontinuation of study treatment, additional treatment will be at the discretion of the treating physician, and patients will continue in long-term follow-up on the study.
-  For Arms 1-4: Patients will receive study product as the number of intradermal injections required to reach the number of cells per dose with no more than 0.1 mL per injection (approximately 4-6 injections). Patients should remain on site for 30 minutes following each vaccination for observation of adverse events.
-  For Arms 1-3 only.
-  Includes eye exam for dry eyes, lymph node and joint assessment and skin exam for vitiligo and rashes.
-  AEs should be recorded from first dose through four weeks following the last dose of study medication regardless of the causal relationship to the study medication. AEs considered related to study medication should be recorded at any time regardless of when they occurred.
-  Samples to be collected prior to dosing
-  Cystoscopy/Cytology for disease recurrence per SOC (approximately every 3 months for 2 years then every 6 months for up to a year). Patients who are determined to have evidence of disease will have SOC treatment per the discretion of the investigator and will continue in long-term follow-up on the study.
-  Weekly study evaluations should be completed within  $\pm 3$  days of the target visit date.

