### 6.3 Long-term Follow-up Visits

All patients will be followed for the procedures listed below every 3 months from the date of the previous visit for 2 years then every 6 months from the date of the previous visit for a year or until study termination, whichever occurs first:

- Survival
- New anticancer treatments initiated after disease recurrence
- TURBT or fulguration procedures
- Cystectomy

In addition patients who have completed all study treatments or have discontinued study product dosing due to reason other than disease recurrence/progression will have the following procedures performed at each long-term follow-up visit:

- Cystoscopy/Cytology; biopsy if area suspicious for disease recurrence is identified at discretion of investigator (*Note: patients who have a biopsy performed will provide at least 4, non-stained, 10 micron sections for TCR sequencing and analysis of infiltrating T-cells.*) *If slides are not available, FFPE tissue (≥50 microns) is also acceptable.*

If a patient has recurrent/progressive disease and discontinues study treatment, the above disease assessment procedures will be discontinued, and subsequent long-term follow-up visits may be conducted via phone visit.

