8.2 Adverse Events

TEAEs will be defined as events that occur on or after the first dose of study medication. The Medical Dictionary for Regulatory Activities (MedDRA) coding dictionary will be used for the coding of AEs (version 18.0 or higher). The severity of TEAEs will be graded on a scale of 1 to 5 according to the adult NCI Common Terminology Criteria for Adverse Events (CTCAE version 4.0) where higher grades indicate events of higher severity. Adverse events will be summarized by grade according to the worst grade experienced. TEAEs, serious or CTCAE grades -5 TEAEs, and TEAEs related to therapy will be summarized overall and by system organ class and preferred term by treatment group. A listing of AEs leading to treatment discontinuation including the patient number, site, treatment group, start date and study day of AE, severity, relationship to study regimen, action taken, and outcome of AE will be provided. Additional summary table summarizing preferred term may be provided if warranted.

For summary purposes, AEs will be defined as all reported events with a start date on or after Study Day 1. All AEs are collected through 30 days post last dose (treatment-emergent AEs). All AEs will have their relationship to study drug (BCG or HS-410) assessed by the investigator as related or not related. Adverse events will be categorized and summarized according to their highest relationship to study drug.

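### Long-term follow-up has no scheduled AE, SAE or new-malignancy question, although related AEs are recordable at any time and any new primary cancer is an SAE

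*Protocol*

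**What the plan says.** **Reporting duties.** Protocol 11.8.3 reads: "Any new primary cancer must be reported as an SAE". It gives no time limit and no causality condition. On related events, the Phase 2 schedule footnote says: "AEs considered related to study medication should be recorded at any time regardless of when they occurred". The Phase 1 schedule footnote and 11.8.5 say the same. The opening paragraph of 11.8 sets the general limit: "AEs should only be recorded for up to four weeks following the last dose of study medication, unless the AE is considered related".

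**Follow-up content.** Section 6.3 states: "All patients will be followed for the procedures listed below every 3 months from the date of the previous visit for 2 years", followed by half-yearly contact for a further year. The list for all patients is survival, "New anticancer treatments initiated after disease recurrence", TURBT or fulguration, and cystectomy. Patients who completed treatment, or stopped it for a reason other than recurrence or progression, also have cystoscopy and cytology. After recurrence or progression with treatment stopped, "subsequent long-term follow-up visits may be conducted via phone visit".

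**Schedules (6.1.1 and 6.2.1).** The adverse-event row is marked up to the EOT visit (Week 29 in Phase 1, Week 56 in Phase 2) and is blank under long-term follow-up. Only cystoscopy/cytology and a row for survival and later therapy are marked there.

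**SAP 8.2.** It says "All AEs are collected through 30 days post last dose (treatment-emergent AEs"). The same section defines TEAEs, and AEs for summary, by a start date on or after first dosing, with no upper limit.

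**The concern.** The protocol creates two duties that can extend past the four-week window, and its follow-up schedule gives sites no prompt to meet them. The nearest item in 6.3, new anticancer treatment, is limited to treatment after disease recurrence. As 6.3 is worded, a patient treated for a second cancer without a bladder recurrence falls outside it.

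The causality condition does not fill the gap. Under 11.8.5 an event counts as related only if it is linked in time to dosing and a direct association can be shown. A cancer or autoimmune event arising long after the last dose may not be judged to meet that, so it would not enter through the rule for related events.

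Protocol 1.4 says this is the first trial to dose patients with this product, and 1.3 describes it thus: "Vesigenurtacel-L is a whole cell vaccine that has been irradiated to render cell replication incompetent while maintaining biological activity". The trial already keeps contact with patients for years. If those contacts ask nothing about new cancers or related events, a low count of late events in the report could reflect either few events or few questions, and a reader could not tell which.

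**Working it through.** The plan gives no figure for this point, so there is none to reproduce. The check sets the passages side by side and then sizes the unprompted period.

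**1. Duty against collection tool**

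| Event after EOT | Duty | Scheduled prompt in follow-up |
|---|---|---|
| Related AE or SAE | 11.8, 11.8.5 and both schedule footnotes: no time limit | None |
| New primary cancer, judged unrelated | 11.8.3: SAE, no time stated; 11.8: unrelated AEs close at four weeks | None in 6.3; the schedule row on later therapy might reveal its treatment |
| Death | Survival in 6.3; deaths are a safety variable in SAP 8 and are listed with cause in SAP 8.3 | Yes |

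**2. Inputs for the size of the gap**
- Last scheduled AE question, for a patient who completes treatment: Day 197 in Phase 1 (6.1.3.10) and Day 386 in Phase 2 (6.2.3.14).
- Follow-up: quarterly for 2 years, then half-yearly for 1 year, so 3 × 365 = 1,095 days.
- The start of the three years can be read two ways. Section 6.3 counts from the previous visit, which suggests after EOT. Section 10.1 counts the quarterly assessments across treatment and follow-up together, which suggests from treatment start.

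**3. Share of planned observation with no scheduled AE question**

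Reading A, three years after EOT: share = 1,095 / (EOT day + 1,095).
- Phase 2: 1,095 / 1,481 = 73.9%
- Phase 1: 1,095 / 1,292 = 84.8%

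Reading B, three years from treatment start: share = (1,095 − EOT day) / 1,095.
- Phase 2: 709 / 1,095 = 64.7%
- Phase 1: 898 / 1,095 = 82.0%

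**4. Contacts without an AE item**
- Reading A: 24/3 + 12/6 = 8 + 2 = 10 in either phase.
- Reading B, Phase 2: (730 − 386)/91.25 + 2 = 5.8, about 6.
- Reading B, Phase 1: (730 − 197)/91.25 + 2 = 7.8, about 8.

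**5. Patients concerned.** The collection gap applies to all 110 planned patients. Of these, 10 + 3 × 25 = 85 are planned to receive vaccine and 25 placebo.

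**6. SAP window.** SAP 8.2 stops collection at 30 days, against four weeks (28 days) in the protocol. The two-day difference is minor. The larger mismatch is that the 30-day sentence has no provision for the protocol's unlimited rule on related AEs, while the TEAE and AE definitions in the same section would admit such events.

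**The case against.** Several provisions soften the point, and some stronger readings do not survive them.

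- **That follow-up collects no safety information at all.** A reader might infer this from the blank adverse-event row. Survival is collected, and the SAP analyses deaths as a safety variable. What is missing is a prompt for non-fatal events.
- **That late events could surface only by chance.** Section 11.8.5 requires observed and spontaneously reported AEs to be recorded and says in general terms that each patient will be questioned about AEs. Section 5.1.2 has the DMC convene for related Grade 3 or higher events throughout the study, and many patients still attend for cystoscopy. These provisions stand. However, the questioning line is tied to no visit, 11.8 ties detection to occasions with a safety evaluation, and follow-up lists none.
- **That a second cancer cannot be detected.** The long-term schedule row on later therapy is not limited to treatment after recurrence, so it might reveal one. Section 6.3 does carry that limit; the two differ, and neither asks about a new cancer directly.
- **That 11.8 and 11.8.3 flatly contradict each other.** Section 11.8.3 states no time frame. It can be read as classifying new cancers as serious, with 11.8 setting the period. This is an unresolved ambiguity, not a proven contradiction.
- **That the safety analysis must end at 30 days.** The open-ended definitions in SAP 8.2 would admit a later related AE once it is recorded. The section is inconsistent, not closed.
- **That late harm is expected.** The documents give no rate. The cells are described as unable to replicate, and Protocol 1.4 reports no treatment-related serious event among 18 patients given a related product.

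The study procedures manual, which 11.8 cites for AE and SAE detection, is not among the documents reviewed and may contain a prompt. That would help sites, but it would not settle the wording in 6.3, the schedules or the SAP.

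**Conclusion.** The point holds as a gap in scheduled collection. After EOT, non-fatal related AEs and new primary cancers depend on spontaneous report or investigator initiative. This covers about 65% to 74% of planned observation in Phase 2 and 82% to 85% in Phase 1, or about 6 to 10 and 8 to 10 contacts, depending on when the three years start. These shares assume completed treatment, 365-day years and follow-up that runs its full length; study termination would shorten it.

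Two wording problems go with it: whether an unrelated new cancer beyond four weeks is reportable, and which window SAP 8.2 applies. The documents do not allow an estimate of how many events would be missed, and the primary endpoint is not affected. The case for change is that the remedy is cheap and alters what is collected.

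**What to change.** 1. **Protocol 6.3 and the long-term column of 6.1.1 and 6.2.1.** Add two items to each existing visit or phone contact: (a) any new primary malignancy, regardless of causality; (b) any AE or SAE since the last contact considered related to study product.
2. **Protocol 11.8.** Reconcile it with 11.8.3 by stating that new primary cancers are exempt from the four-week limit.
3. **SAP 8.2.** Align the 30-day sentence with the protocol's four-week and any-time rules. Tabulate late related events and new malignancies by arm, descriptively and separately from on-treatment TEAEs.

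The cost is two eCRF questions per contact, one sentence in 11.8 and one extra table, with no added visit, staff or procedure. With 25 patients per Phase 2 arm, the table supports description only, not inference between arms.

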### 11.8.4 Clinical Laboratory Abnormalities and Other Abnormal Assessments as AEs and SAEs

Abnormal laboratory findings (e.g., clinical chemistry, hematology, and urinalysis) or other abnormal assessments (e.g., ECGs or vital signs) that are judged by the investigator as **clinically significant** will be recorded as AEs and SAEs if they meet the definition of an AE or SAE. Clinically significant abnormal laboratory findings or other abnormal assessments that are detected during the study or are present at baseline and significantly worsen following the start of the study will be reported as AEs or SAEs.

However, clinically significant abnormal laboratory findings or other abnormal assessments that are associated with the disease being studied, unless judged by the investigator as more severe than expected for the patient's condition, or that are present or detected at the start of the study and do not worsen, will **not** be reported as AEs or SAEs.

The investigator will exercise his or her medical and scientific judgment in deciding whether an abnormal laboratory finding or other abnormal assessment is clinically significant.

#### **11.8.5 Reporting Adverse Events**

The investigator will record all directly observed AEs and all AEs spontaneously reported by the study patient on the *Adverse Event* ECRF. In addition, each study patient will be questioned about AEs.

Each AE should be described in detail on the *Adverse Event* ECRF and SAEs on a *Serious Adverse Event* form and include the following information: start and stop dates, CTCAE v. 4.03 grading, relationship to study medication, action taken, and outcome. AEs should be recorded from time of first dose up to four weeks following the last dose of study medication regardless of the causal relationship to the study medication. AEs considered related to study medication should be recorded at any time regardless of when they occurred.

The investigator will also assess the possible relationship between the AE and the study medication as well as any concomitant medications according to the following criteria:

- Related: AE and administration of study product are related in time, and a direct association can be demonstrated.
- Not related: AE is clearly explained by another cause not related to study product.

Event outcome will be recorded using the following categories:

- Recovered/resolved
- Not recovered/not resolved
- Recovered/resolved with sequelae
- Fatal
- Unknown

